9.1.5 Laboratory Accreditation and Reference Ranges

The Investigator and the Sponsor will maintain a copy of the laboratory accreditation and the reference ranges for the central laboratory used for clinical laboratory evaluations.

9.2 Study Procedures and Evaluations

Please see the Schedule of Activities presented in [Appendix A](#) for designated time points for assessments.

9.2.1 Clinical Evaluations

The following clinical evaluations will be conducted during the course of the study.

- Medical/ophthalmic history and demographics: Relevant medical history (with particular emphasis on previous medical conditions that may lead to exclusion) and significant ongoing medical conditions or diseases should be documented. Ophthalmic history should include treatment history for DR/DME.
- Body System Assessments: Body systems to be evaluated include general appearance, HEENT (head, ears, eyes, nose and throat), cardiovascular, respiratory, abdomen/gastrointestinal (including query of any changes in bowel habit frequency, consistency, or color), musculoskeletal, and skin (including query of any skin abnormalities noted as well as direct observation of skin of head, neck, chest, abdomen, back and extremities). Subjects will be instructed that if they note any abnormalities between visits they should contact their study doctor so that any such findings can be assessed.
- Height (at Screening only), weight, and temperature
- 12-Lead ECG: A standard 12-lead ECG will be obtained after the subject has been resting comfortably in a supine position for approximately 5 minutes and prior to vital sign assessments and blood draws when possible. With the subject in a supine position, obtain the 12-lead tracing. Each 12-lead ECG must be recorded with a paper speed of 25 mm/sec and printed as a paper copy. The Investigator (or a qualified observer) will interpret the ECG and record the results including the following parameters: heart rate, PR interval, QT interval, QRS interval, and QTcF (corrected).

In some cases, it may be appropriate to repeat abnormal ECGs to rule out improper lead placement as contributing to the ECG abnormality. It is important that leads are placed in the same positions each time in order to achieve precise ECG recordings. If a machine-read QTcF value is prolonged, repeat measurements may not be necessary if a qualified physician's interpretation determines that the QTcF values are in the acceptable range.

All abnormal rhythms will be reviewed by the study physician for the presence of rhythms of potential clinical concern. The Investigator should utilize medical judgment in the reporting of AEs and SAEs as well as determination of additional cardiac work-up. A printed record of the tracing(s) of the clinically significant rhythm(s) will be made and retained with other source documents. An ECG will be performed at the Screening, Month 6, and Month 12 (EOT) visits.

- Vital Signs: Vital signs include blood pressure and heart rate. Vital sign assessments should be taken prior to blood draws when possible. The subject should be seated, with legs uncrossed and feet resting comfortably on the floor, for at least 5 minutes prior to measuring blood pressure and heart rate.
- ETDRS Best Corrected Visual Acuity (BCVA): Visual acuity of both eyes will be assessed using the ETDRS protocol at 4 meters.
- Slit Lamp Biomicroscopy: Slit-lamp biomicroscopy will include examination of the cornea, conjunctiva, anterior chamber, iris/pupil, lens, and eyelid of both eyes. Findings

will be graded as normal, abnormal not clinically significant, or abnormal clinically significant.

- Intraocular Pressure (IOP): IOP will be assessed with either applanation tonometry or tonopen; the method should be consistent throughout the study.
- Dilated Indirect Ophthalmoscopy: Dilated indirect ophthalmoscopy will be performed to assess the vitreous, macula, optic nerve, and peripheral retina of both eyes. Findings will be graded as normal, abnormal not clinically significant, or abnormal clinically significant.
- SD OCT: Spectral domain optical coherence tomography (SD OCT) will be utilized to assess retinal characteristics of both eyes. The OCT instrument type used throughout the study must be consistent for an individual subject. OCT imaging data will be transmitted to a central reading center for independent analysis. Detailed instructions for imaging and data transfers will be provided in the study-specific imaging manual.
- Fundus Photography: Modified 7-Field or 4-Wide Field color fundus photographs (including red free images) of both eyes will be taken to evaluate retinal anatomy. Photographs will be transferred to a central reading center. Detailed instructions for imaging and data transfers will be provided in the study-specific imaging manual.
 - For sites participating in the UWF imaging sub-study, *in addition to* Modified 7-Field or 4-Wide Field color fundus photographs, UWF color fundus photographs should be taken using the Optos P200Tx or Optos California system. Parameters obtained are detailed further in this section under “UWF imaging”.
- Fluorescein Angiography (FA): Retinal vasculature of both eyes will be evaluated by fluorescein angiography (FA). FA images will be transferred to a central reading center. Detailed instructions for imaging and data transfers will be provided in the study-specific imaging manual.
 - For sites participating in the UWF imaging sub-study, *in lieu of* standard FA, UWF FA images should be taken using the Optos P200Tx or Optos California system. Parameters obtained are detailed further in this section under “UWF Imaging”.
- Adverse Event Assessments: Beginning with informed consent and through final protocol required visit, the Investigator and study personnel will review each subject's laboratory and clinical evaluation findings and query the subject directly regarding AEs (see [Section 10](#)). If a home healthcare nurse identifies any potential AEs during a home visit, the nurse will communicate directly to the study site and the Investigator will be responsible for determination of AEs and any necessary follow-up with the subject. Subjects must be followed for AEs until the final required protocol visit or until all drug-related toxicities and serious adverse events have resolved (or are considered chronic/stable), whichever is later.
- Concomitant Medication Recording: All medications, both prescription and non-prescription, and including vitamins, herbals, topicals, inhaled, and intranasal, taken within 30 days prior to the start of study medication and through the Month 12 EOT visit

should be recorded on the appropriate CRF. At each study visit, subjects will be asked whether they have started or discontinued any medication since their previous study visit. This includes single use or PRN (as needed) medication use. All medications and treatments, including vitamin supplements, over-the-counter medications, and oral herbal preparations must be recorded in the CRFs.

- Exploratory Efficacy Sub-Study Evaluations (to be conducted at a subset of sites):
 - OCT-A – OCT-angiography should be obtained from both eyes using a SD OCT machine according to instructions provided by the manufacturer
 - ERG – Flicker ERGs will be obtained from both eyes using the RETeval system (LKC Technologies, Gaithersburg MD). Responses will be obtained from electrodes placed on the skin under light-adapted conditions. Parameters obtained will include flicker ERG amplitude, ERG peak latency, and pupillary response to each of 3 different flicker intensities. RETeval score will also be derived from these data (Maa et al, 2015).
 - UWF imaging – UWF FA and UWF color fundus photographs will be obtained using the Optos P200Tx or Optos California instrument following procedures specified in the study specific imaging manual. As described previously, UWF FA will be performed *in lieu of* standard FA, but UWF photographs will be obtained *in addition to* standard Modified 7-Field or 4-Wide Field color fundus photographs. UWF fundus photographs are only obtained on visits when UWF FA is performed (e.g. Screening, Month 6, and Month 12 (EOT). Parameters obtained from UWF FA include area of peripheral non-perfusion, area of peripheral leakage. Parameters measured in UWF color fundus photographs include peripheral microaneurysms, vitreous hemorrhage, venous beading, intra-retinal microvascular abnormalities (IRMA) and neovascularization elsewhere (NVE).

9.2.2 Laboratory Evaluations:

All samples collected (with the exception of urine pregnancy tests) will be sent to a central clinical laboratory.

If to be conducted at the same time points, blood sampling should occur after vital sign assessments and ECGs have been conducted.

Samples for clinical laboratory evaluations (hematology, chemistry, fecal occult blood testing, and urinalysis assays) and Screening serum pregnancy tests will be analyzed at the central laboratory. The Investigator is responsible for reviewing laboratory results for clinical significance.

The central laboratory is also responsible for distribution of PK samples to the respective PK laboratory for analysis. Once the results of the study are known, the Sponsor will determine if biomarker and genetic analyses will be conducted and will direct the central clinical laboratory on distribution of samples for biomarker and genetic analyses to the appropriate laboratories.

The following clinical laboratory evaluations will be conducted during the course of the study:

- Pregnancy test: A serum pregnancy test will be performed at Screening for females of childbearing potential. The investigative site will perform a urine pregnancy test at the Baseline, Month 6 and Month 12 EOT visits. The Screening and Baseline results must be available and must be negative before the subject takes the first dose of any study medication on Day 1. At each monthly visit, the site will query subjects of childbearing potential regarding the potential for pregnancy.
- Hematology: The complete blood count (CBC) will include: hemoglobin (Hgb), hematocrit, red blood cell (RBC) count, mean corpuscular (cell) volume (MCV), mean corpuscular hemoglobin (MCH), mean corpuscular hemoglobin concentration (MCHC), red cell distribution width (RDW), mean platelet volume (MPV), white blood cell (WBC) count with differential (neutrophils, immature granulocytes, lymphocytes, monocytes, eosinophils, basophils), platelet count, reticulocyte count and HbA1C. Hematology will be assessed every other month except for HbA1C which will be assessed at Screening, Baseline, Month 6, and Month 12 (EOT) visits.

Chemistry: The serum chemistry will include the following assays: sodium, potassium, bicarbonate, chloride, calcium, phosphorus, glucose, creatinine, blood urea nitrogen (BUN), creatinine phosphokinase (CPK), uric acid, albumin, total protein, total bilirubin, alkaline phosphatase, alanine transaminase ((ALT (SGPT)), aspartate transaminase (AST (SGOT)), lactate dehydrogenase (LDH), total cholesterol, triglycerides, ferritin, serum iron, total iron binding capacity (TIBC) and transferrin saturation (TSAT). Chemistries will be assessed monthly. eGFR will be determined on serum chemistry samples collected at the Screening, Baseline, Month 6, Month 9, and Month 12 (EOT) visits.

- Fecal occult blood testing: A small amount of stool will be collected on 3 separate days as per standard procedure to measure fecal blood levels using the HemoQuant test ([Rockey et al, 1999](#); [Barber et al, 2002](#); [Harewood et al, 2002](#)). At the Screening, Month 6, Month 9, and Month 12 (EOT) site visits, Investigative sites will distribute instructions and supplies for home specimen collection to the subject. For 3 days prior to and during the days of stool sample collection, subjects will refrain from eating red meat and taking high dose aspirin as detailed in Section 9.1.4. Subjects will collect their specimens and are responsible for shipping to the central laboratory for testing; specimen collection and shipping should be conducted within one week following the site visit.
- Urinalysis: Urinalysis will include bilirubin, blood, glucose, ketones, pH, protein, specific gravity and microscopic examination (only if urinalysis is positive for blood or protein).
- Urine-albumin-to-creatinine ratio (UACR): UACR will be determined on urine samples collected at the Baseline, Month 6, Month 9, and Month 12 (EOT) visits; subjects should refrain from heavy exercise 24 hours before these visits.
- Pharmacokinetic analysis: Analysis of plasma samples for AKB-9778 concentration determinations will be performed by a central PK laboratory using a validated Liquid Chromatography-Mass Spectrometry and Liquid Chromatography-Tandem Mass Spectrometry (LC-MS/MS) method. Detailed instructions for processing and shipment of samples will be provided by the Sponsor or Central laboratory

- Biomarker analysis in Plasma: Biomarkers will be assessed in plasma samples. Detailed instructions for processing and shipment of samples for biomarker analyses will be provided by the Sponsor or Central laboratory.
- Genetic analysis: Detailed instructions for processing and shipment of samples for biomarker analyses will be provided by the Sponsor or Central laboratory.

9.3 Schedule of Activities

The Schedule of Activities is presented in [Appendix A](#) and shows the timing of planned study procedures to be conducted at the study site and at the home care nursing visits. Every effort should be made to adhere to the procedure schedule and all assessments should be completed at each study visit.

The Screening, Baseline, Treatment, and Follow-up Periods will require subject participation for approximately 56 weeks.

Study procedures, clinical assessments (including laboratory assays), and PK, biomarker and genetic sampling will be performed as indicated in the Schedule of Activities.

Subjects will be responsible for self-administration of study medication which is provided in prefilled sterile syringes. The subject will self-inject BID on a morning and evening schedule as detailed in [Section 8.3.5](#). Subjects will dose BID with the exception of Day 1 when the subject will dose the first (AM) dose at the clinic and will begin the BID dosing schedule on Day 2. No PM dose will be taken on Day 1.

At the visit on Day 1, the site will train the subject on SC study medication administration and dosing diary completion. After the pre-dose activities have been completed, the subject will self-administer the AM dose of study medication.

After the subject has completed the EOT visit, no further subcutaneous dosing will occur.

Study visits on Day 1, Month 6 and Month 12 EOT should be scheduled for the morning. The remainder of the site visits should also be scheduled for the morning when possible. Subjects will maintain a daily study medication diary and will record timing and location of dose.

At the site visits on Day 1 and Months 1 through 11, subjects will be dispensed subcutaneous study medication and dosing supplies.

Subjects discontinuing study medication sooner than the planned 12-month dosing period or withdrawing from the study should complete the Month 12 EOT assessments including the EOT assessments at the EOT site visit (See [Section 9.3.2.16](#)) and the EOT homecare nurse visit (See [Section 9.3.3.5](#)).

Detailed descriptions of procedures and activities to be followed during each site and homecare nurse visit are presented in the following sections. For specific time points please refer to the Schedule of Activities in [Appendix A](#). Procedures and activities to be conducted at the investigative site are presented in [Section 9.3.2](#) followed by procedures to be conducted at the homecare nurse visits presented in [Section 9.3.3](#).

9.3.1 Visit Windows

Plasma PK samples collected at 30 and 90 minutes after dosing of study medication on Day 1 and Month 6 should be collected within ± 10 minutes of the target time. If for any reason, the sampling time point for a given sample falls outside of the visit window, the sample must still be collected. For all samples; the exact time of sample collection will be recorded.

Blood pressure and heart rate evaluations performed must be conducted within ± 20 minutes of the designated time.

Subjects will only use AM syringes for dose administration in the morning and PM syringes for dose administration in the evening. Subjects should administer their daily doses around the same time every morning and evening, if possible. If a dose is missed, this dose should be skipped and the subject should maintain the morning and evening dosing schedule.

The Day 7 phone call must be conducted within ± 3 days.

Site visits scheduled for Months 1 through 12 should be conducted within 28 days times the study month number ± 3 days relative to the baseline visit (e.g. Month 1 visit window is 28 ± 3 days from Day 1, Month 2 visit window is 56 ± 3 days from Day 1, etc.).

Homecare nurse visits scheduled for Screening, Months 3, 6, 9 and 12 should be conducted within 1 week after the corresponding site visit. The Follow-up homecare visit occurs 4 weeks ± 3 days after the EOT visit at the site.

The fecal occult blood specimen collection and shipping to the Central Laboratory should be conducted by the subject within the week following the corresponding site visit.

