In the 9-month dog toxicity study, broadly distributed dermal-localized nodules were observed on all dogs at 15 and 30 mg/kg/day and one nodule was observed on one male dog at 6 mg/kg/day. The majority of nodules were identified microscopically as focal angiectasis, characterized as ectatic, blood-filled vessels with varying degrees of thrombosis that was occasionally associated with papillary endothelial hyperplasia; and one nodule in a high dose dog identified as benign hemangioma. The nodules ranged in size between 1 and 50 mm in diameter and appeared to slowly enlarge or remain static in size. The majority of nodules were persistent, but a few nodules were self-limiting while AKB-9778 dosing continued. The dermal nodules were observed to rapidly resolve upon drug withdrawal. In addition, largely GI tract-localized minimal to mild angiectasis was observed by microscopic examination at all dose levels in dog (at exposures 6- to 24-fold the human exposure at 15 mg BID) and not present in the vehicle control group. The vascular findings were not associated with any clinical observations, serum chemistry, or other microscopic changes. In the rat 6-month study, minimal focal angiectasis was observed by microscopic examination in the uterus with cervix of one high-dose rat (at higher AUC exposure than exposures assessed in dog) and was considered incidental. There were no skin nodules or GI-related findings in rat. In the 9-month monkey study, a solitary dermal nodule on the tail of one high dose animal was characterized as angiectasis with resolving thrombosis, and associated with AUC exposure higher than exposures assessed in dog. There were no GI-related findings in monkey. These observations suggest an increased sensitivity of the dog to vascular effects of AKB-9778. No unusual or unexpected dermal findings have been observed in clinical studies with AKB-9778. For guidance on assessment and monitoring of potential vascular effects refer to the Investigator's Brochure.

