Dermal nodules, characterized microscopically as angiectasis (dilated, blood filled vessels), have been observed in the chronic 9-month dog toxicity study and with a single incidence in one high-dose monkey in the chronic 9-month monkey study; however, no unusual dermal findings have been observed in human clinical studies of durations of up to 3 months. Whether ectasias will be seen when patients are dosed for longer periods is unknown. In the chronic dog study, angiectasis was also identified microscopically largely in the GI tract after the 9-month dosing period. These changes were asymptomatic (i.e. there was no bleeding, loss of appetite, or other observable clinical abnormalities of the GI tract) at exposures up to 24-fold above the human clinical exposure.

The current clinical study employs robust safety monitoring to assess for potential adverse effects. Safety assessments in the current study include body system assessments, vital sign monitoring, clinical laboratory assessments (including blood chemistry, hematology, fecal occult blood testing, and urinalysis), vision and ocular assessments.

On an ongoing basis throughout the conduct of the study, a variety of planned safety monitoring reviews of available study data will be conducted (as detailed in Section 6.4 Oversight of Safety and in the [AKB-9778 Safety Surveillance Plan](#)). These include weekly reviews conducted by the

Aerpio Medical Monitor, monthly masked reviews by the Aerpio Clinical Safety Review Team (CSRT), and quarterly masked reviews by the Safety Assessment Committee (SAC: composed of members independent of the clinical team including Aerpio physician cardiologist, a non-sponsor independent physician experienced in the assessment of clinical trial safety data, a non-sponsor independent physician with expertise in gastrointestinal/hepatology safety assessment, and a non-sponsor independent physician/ophthalmologist with expertise in ophthalmology safety assessment).

Given the safety history of AKB-9778 and the robust safety monitoring implemented in this study, there is anticipated to be minimal risk of drug-related severe adverse effects as a result of participation in this study.

In nonclinical reproductive toxicology studies (rats and rabbits), AKB-9778 was not associated with embryo-fetal abnormalities. Additionally, in the chronic repeated-dose rat (6-month) and dog (9-month) toxicity studies, there was no evidence of reproductive organ toxicity.

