9 STUDY PROCEDURES AND SCHEDULE OF ACTIVITIES

Please see [Appendix A](#) for a detailed table of the Schedule of Activities.

A one-month duration in this study is defined as 4 weeks/28 days. The 12-month Treatment period is 48-weeks/336 days.

This study includes the following periods and visits:

- Screening visit (up to 28 days prior to Baseline)
- Baseline visit (pre-dosing period on Day 1)
- Treatment Period (Days 1 through Month 12 (Week 48)); including:
 - Investigative site visits on Day 1, Day 7 (phone-call), and monthly (i.e., every 4 weeks) thereafter until the Month 12 (Week 48) EOT visit
 - Homecare nurse visits on Screening and Months 3, 6, 9, 12 (EOT)
- Follow-Up Period 1 Month (4 weeks) Post-Treatment

The following sections describe the procedures to be completed during the study. Subjects are to be assessed by the same Investigator or site personnel whenever possible.

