9.3.2.16 Treatment Period – Month 12 End of Treatment Visit (Week 48)

- 12 Lead ECG (prior to vital signs and blood draws)
- Weight and temperature
- Vital signs
 - sitting blood pressure and heart rate measurements
- Eye and Vision Exams:
 - ETDRS BCVA
 - slit-lamp biomicroscopy
 - intraocular pressure
 - dilated indirect ophthalmoscopy
 - SD OCT
 - fundus photography (and UWF fundus photography at select sub-study sites)

- fluorescein angiography (or UWF fluorescein angiography at select sub-study sites)
- ERG (at select sub-study sites)
- OCT-A (at select sub-study sites)
- Laboratory Procedures
 - urine pregnancy test
 - hematology
 - clinical chemistry
 - urinalysis
 - biomarker blood sampling
- AE monitoring and AE recording since last visit
- Concomitant Medication recording as needed since last visit
- Collect returned used supplies and review medication use since last visit
- Dispense instructions and kit for subject to perform home fecal occult blood specimen collection

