18 APPENDICES

18.1 Appendix A: Schedule of Activities

Protocol Activities	Schedule of Activities [A]														F/U EOT + 1M		
	Screening		Baseline		Treatment Period [B]												
	Day		Month														
	Day - 28 to Day - 1	Day 1 Pre-Dose	Day 1	Day 7	M1	M2	M3	M4	M5	M6	M7	M8	M9	M10	M11		
Informed Consent	X																
Eligibility Criteria	X																
Demographics	X																
Medical/Ophthalmic History	X	X														X	
Height Weight and Temperature [C]	X											X				X	
Body System Assessments [D]	X						X				X		X		X	X	
ECG [E]	X										X					X	
Vitals [F]																	
Sitting BP and HR	X	X	X		X	X	X	X	X	X	X	X	X	X	X	X	
Eye and Vision Exams																	
ETDRS BCVA	X	X			X	X	X	X	X	X	X	X	X	X	X	X	
Slit Lamp Biomicroscopy	X	X					X			X			X			X	
Intraocular Pressure	X	X					X			X			X			X	
Dilated Indirect Ophthalmoscopy	X	X					X			X			X			X	
SD OCT	X						X			X			X			X	
Fundus Photography[G]	X						X			X			X			X	
Fluorescein Angiography [H]	X									X						X	
OCT Angiography Sub Study [I]		X					X			X			X			X	
ERG Sub Study [I]		X					X			X			X			X	
Laboratory Procedures																	
Serum/Urine Pregnancy [J]	X	X								X						X	
Hematology[K]	X	X				X		X		X		X		X		X	
Chemistry [L]	X	X			X	X	X	X	X	X	X	X	X	X	X	X	
Urinalysis [M]		X								X			X			X	
Fecal Occult Blood Test [N]	X									X			X			X	
Biomarker Blood Sampling		X														X	
Blood sampling for Genetic Analyses		X															
PK Blood Sampling [O]			X								X						
Dosing [P]				X	X	X	X	X	X	X	X	X	X	X	X	X	
Study medication dispensing & return, diary review [Q]				X		X	X	X	X	X	X	X	X	X	X	X	
AE collection [R] [S]	X	X	X	X	X	X	X	X	X	X	X	X	X	X	X	X	
Concomitant Medication Review [T]	X	X	X	X	X	X	X	X	X	X	X	X	X	X	X	X	

[A] Assessments are conducted at the study site unless otherwise noted.

[B] Site visits scheduled for Months 1 through 12 should be conducted within 28 days times the study month number ± 3 days relative to the baseline visit. Homecare nurse visits scheduled for Screening, Months 3, 6, 9 and 12 should be conducted within 1 week after the corresponding site visit. The Follow-up homecare nurse visit is to be conducted 4 weeks (± 3 days) after the EOT visit at the investigative site.

[C] Height is collected at screening only.

[D] Body system assessments are conducted at the home care nursing visit.

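### No scheduled on-drug skin/body-system exam or stool blood test takes place after Month 9, because both Month 12 readings follow the visit at which dosing ends

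*Protocol*

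**What the plan says.** Direct observation of the skin is part of the body system assessment (Protocol 9.2.1). Appendix A, note D, fixes where it is done: "Body system assessments are conducted at the home care nursing visit". Section 9.3.1 fixes when: "Homecare nurse visits scheduled for Screening, Months 3, 6, 9 and 12 should be conducted within 1 week after the corresponding site visit". The same section has subjects collect and ship stool samples in the week after the matching site visit. The Month 12 site visit list (9.3.2.16) ends with "Dispense instructions and kit for subject to perform home fecal occult blood specimen collection".

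Section 9.3 sets the end of dosing: "After the subject has completed the EOT visit, no further subcutaneous dosing will occur".

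Three other places treat the Month 12 nurse visit as part of treatment. Section 6.1 puts the home visits at three-month intervals within the treatment period. Section 9 lists the Month 12 home visit under that period. The heading of 9.3.3.5 labels it so.

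SAP 5.5 reports body system shifts and stool blood change at Week 48. SAP Table 2 gives both a Week 48 window of Days 295-378 and has no Follow-up row.

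**The concern.** At Months 3, 6 and 9 it does no harm to put the nurse exam after the site visit, because dosing continues. At Month 12 the same order moves the exam and the stool samples past the end of dosing.

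This matters for this compound. On the dog findings, Protocol 4.2 states: "The dermal nodules were observed to rapidly resolve upon drug withdrawal". On human exposure beyond three months, Protocol 4.4.1 states: "Whether ectasias will be seen when patients are dosed for longer periods is unknown". Section 4.4.1 also names body system assessments and stool blood testing among the safeguards of the trial. If a reversible skin lesion first appears between Months 9 and 12, the only later skin exam in the treatment schedule may find it reduced or gone. The Week 48 table would then describe a subject off drug without saying so.

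The SAP adds a second, smaller route to the same problem. In some subjects the follow-up nurse exam, about 4 weeks off drug, can be tabulated as the Week 48 value.

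**Working it through.** **Inputs**
- Treatment length (Protocol 9): "The 12-month Treatment period is 48-weeks/336 days".
- Site visits (9.3.1): "Site visits scheduled for Months 1 through 12 should be conducted within 28 days times the study month number ± 3 days", counted from baseline.
- Nurse exam and stool collection: 0 to 7 days after the site visit (9.3.1).
- Last dose: no later than the EOT site visit (9.3).
- Follow-up nurse visit: 4 weeks ± 3 days after the EOT site visit (9.3.1).
- SAP Table 2: Week 36 window Days 211-294, Week 48 window Days 295-378. Study Day = days after baseline + 1.

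**1. The plan's own figure.** 12 × 28 = 336 and 48 × 7 = 336. It reproduces.

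**2. Last on-drug reading (Month 9).** Nominal: 9 × 28 = 252, plus 0 to 7, gives 252-259 days after baseline. With windows: 252 − 3 = 249 to 252 + 3 + 7 = 262.

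**3. End of dosing.** Nominal 336; with windows 333-339.

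**4. Month 12 readings.** From 333 to 339 + 7 = 346 days after baseline, which is 0 to 7 days after the EOT visit. The stool samples cannot precede EOT, because the kit is issued there. Section 9.1.4 asks for three days of diet restriction first, and 9.2.2 asks for samples on three separate days. Assuming the restriction starts when the kit is issued and the sampling days are consecutive, samples fall about 3-5 days off drug at the earliest.

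**5. Treatment time after the last on-drug reading.**

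| | Shortest | Longest |
|---|---|---|
| Nominal | 336 − 259 = 77 days (77/336 = 23%) | 336 − 252 = 84 days (84/336 = 25%) |
| With windows | 333 − 262 = 71 days (71/336 = 21%) | 339 − 249 = 90 days (90/336 = 27%) |

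**6. SAP Week 48 window.** For completers, the follow-up exam falls between Day 333 + 28 − 3 + 1 = 359 and Day 339 + 28 + 3 + 1 = 371, inside 295-378. The rule below SAP Table 4 prefers the scheduled visit that matches the window, and otherwise takes the observation nearest the target day. The follow-up exam therefore becomes Week 48 in two cases:
- the Month 12 exam is missing;
- a subject stops early, the EOT exam falls before Day 295, and the follow-up falls on Days 295-378. At the nominal 28 days this needs an EOT site visit on or after Day 295 − 28 = 267. Example: site and nurse EOT exams on Day 290 fall in the Week 36 window, and the follow-up on Day 290 + 28 = 318 becomes Week 48.

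The exclusion of unscheduled data in SAP 7.2 does not prevent this, because the follow-up exam is a scheduled visit.

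**The case against.** The other side has good points, and most of them limit the claim.

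- **Other monitoring continues.** A reader might infer that no on-drug safety data exist after Month 9. That is wrong. Adverse events are asked about at Months 10, 11 and 12, hematology is drawn at Months 10 and 12, and chemistry with iron indices is monthly. Subjects are told to call about abnormalities between visits, and the nurse asks about skin changes as well as looking (9.2.1). A lesion that has regressed can still be captured by history. None of these is a direct skin exam or a stool test.
- **A same-day exam is possible.** Within one week after does not exclude day 0, and 9.3.3 allows the nurse visit at the site. Such an exam could fall within hours of the last dose. It is allowed but not required, and it does not help the stool samples.
- **Lesions may not vanish in a week.** A reader might infer that they would. Protocol 4.2 gives no time for the resolution, and the statement covers dermal nodules in dogs only. The plasma half-life of about 1 hour (4.3) shows that exposure ends quickly; it does not set how fast a structural lesion regresses.
- **The gut findings are weaker ground.** The documents give no off-drug course for the gastrointestinal angiectasis, and 4.4.1 reports no bleeding in that dog study. Stool passed soon after EOT may still reflect bleeding on drug.
- **Quarterly spacing is planned.** An interval of about 84 days also separates Months 3, 6 and 9, and the Month 6 and 9 exams already cover dosing beyond three months. True. The difference is that each earlier interval closes with an on-drug reading and the last one need not.
- **The follow-up exam does not displace a completed Month 12 exam.** Correct under the SAP rule. Only the two cases in the working remain. SAP 11 says some data will be summarised for the treatment period and also with follow-up included, but does not name which.

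**Conclusion.** The concern holds for the two named assessments. After Month 9 no on-drug skin/body-system exam or stool blood test is scheduled. The Month 12 exam falls 0 to 7 days after dosing ends, and the Month 12 stool samples come only after EOT. The uncovered stretch is nominally 77-84 of 336 days, or 71-90 with visit windows. Protocol 6.1, 9 and 9.3.3.5, which place the Month 12 nurse visit in the treatment period, do not agree with 9.3 and 9.3.1 and must be reconciled with them.

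The supported consequence is that a reversible skin lesion arising after Month 9 could be missed or under-graded. The documents do not show that it would be lost, and they give no basis for the same statement about gut findings. The result assumes that subjects dose up to the EOT visit and that visits keep their windows. The SAP window problem is separate and limited to subjects with a missing Month 12 exam and some early stoppers. It concerns the body system exam only, since no stool test is scheduled at follow-up.

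**What to change.** **Protocol 9.3.1, 9.3.2.15, 9.3.2.16, 9.3.3 and Appendix A notes B and N.** Hold the Month 12 nurse exam on the day of the Month 12 site visit, or in the week before it, while the subject is still on study medication. Dispense the Month 12 stool kit at Month 11, for collection before EOT. This brings the visit into line with 6.1, 9 and 9.3.3.5 and leaves the dosing rule untouched. The exam would fall nominally on Days 330-337 (337 − 7 = 330), still inside the Week 48 window.

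**SAP Table 2.** Add a Follow-up row, and exclude the post-EOT follow-up exam from the Week 12-48 windows.

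**Reporting.** Show days since last dose with the Week 48 body system and stool results.

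**Cost.** A protocol amendment, earlier booking of one nurse visit, and a kit kept at home for up to about four weeks. An exam in the week before EOT gives up at most 7 of 336 days of exposure (2%). No visit or procedure is added. Subjects who stop early gain nothing from the re-timing, and for them the as-soon-as-possible rule stays. If visits can no longer be moved, the SAP change and the reporting of days since last dose are still available and need no new data.
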